## Phase 2 Protocol

This study is designed to understand how coaching versus standard education impacts pediatric providers' recommendation of the etonogestrel contraceptive implant to adolescent girls considering contraception.

A cohort of 100 providers will be recruited. A pediatric provider is defined for this study as an MD, DO, PA, or APRN who is fully licensed in the state of Florida and graduated with the degree. To participate this individual must have a practice that provides care to female patients under the age of 18 in a pediatrics, family medicine, internal medicine or obstetrics/ gynecology practice that refers patients for or provides contraception in their practice. The provider must devote at least 50% of their practice to primary care or reproductive health. A provider can also see patients 18 years of age and older. More than one provider in a practice may participate. A minimum of 30% APRN or PA providers will be recruited.

By participating in the study, the pediatric provider is agreeing to participate in a 6-month long educational experience for the provider.

The cohort will be randomized into two groups. The control group is comprised of providers who will receive an educational activity and tip sheet. The experimental group is comprised of providers who will receive an educational activity and tip sheet plus an at-will coaching resource. Both groups will receive the educational activity together in a virtual platform as well as the same written tip sheet at the end of the educational activity. Both groups will be administered the same pre-test and post-test at beginning and end of educational activity via a redcap survey.

The educational activity was created based on Phase 1 of this study which identified the most common barriers in providing etonogestrel contraceptive implant to adolescents who reside in North & Central Florida and the areas of highest knowledge deficit. Topics included in this program are:

- Best practices in contraception counseling for teens
- Adolescent attitudes towards the contraceptive implant
- Parental attitudes towards the contraceptive implant
- Cost and access to contraception
- Physical characteristics of the contraceptive implant
- Indications and contraindications to receiving the contraceptive implant
- Understanding the implant placement procedure
- Most common side effects of the contraceptive implant
- Menstrual bleeding profile following placement of the implant
- Management of common side effects of the contraceptive implant
- Reasons to discontinue the contraceptive implant.

While participants in Phase 1 can participate in Phase 2 it is not required to have participated in Phase 1. Additionally, Phase 1 participants will not be directly contacted to participate in Phase 2. Instead, participants will be recruited through their response to a flyer and outreach done by the sponsoring institution's Education Events Office. After expressing interest in the educational event, providers will be contacted by email to determine if they are interested in participating in the study. If they are they will provide a phone number where staff can contact them staff to confirm their eligibility to participate in the study and seek their informed consent for participation in the study. Providers are welcome to participate in the educational session and receive continuing medical education credits regardless of their decision to participate in the study. If providers consent to participate in the study, they will receive an electronic copy of the informed consent that they can sign via DocuSign. The total educational session will be 1.5 hours with one hour dedicated to providing the educational session, questions and answers and 30 minutes dedicated to explaining the study and protocol. All study participants will receive 1 hour of continuing medical education credit for their participation in the educational event provided by the

sponsoring institution. Additionally, study participants who are physicians and hold board certification can elect to receive Part 4 Maintenance of Certification credit by participating in the activity. The educational session will occur virtually to mitigate the risk of contracting COVID 19 as well as include participants more widely in the state of Florida.

Each participant will receive an educational packet that will include: the slides and a troubleshooting tip sheet mailed to them prior to the date of educational event. The trouble shooting tip sheet will have the key take away points from the educational program. Participants who have consented to the study will additionally receive a contraception discussion tracking form, that will be color coded and labelled for each month of the study to indicate whether the participant has been randomized to the control group or the experimental group. As well as instructions on how to enroll in the MOC program. The referral form will have an email address at the bottom that the participant should use to return in their contraception discussion tracking forms. The tracking form will have the participant for each day record the number of patients under 18 who they discussed contraception with, the number who chose the implant, the number who chose another reliable contraceptive method, and number who chose no option. There will also be a place for the provider to record any reflections or questions they have. Each week participants will receive an email reminding them to enter the information from the tracking form into the MOC portal. They will receive a survey on months 2,4, and 6 via red cap asking them about practice changes and challenges experienced while trying to implement increased counseling. For participants in the experimental group their tip sheet has an email address they can use to access coaching. Additionally, this email will be included in all communication reminding them to enter their tracking form information into the MOC portal. Coaching is at will and is initiated by sending an email with a non-emergent question that will be answered within two business days. If the principal investigator is on vacation or unavailable, then the participant will be notified that coaching is not available and that they should proceed as they typically would without coaching. Questions will be categorized as to whether they are related to: indication, procedure question, post-placement bruising, post-placement breakthrough bleeding, post-placement weight gain, other post-placement side effect. These categories were selected based on data from Phase 1 questionnaire that showed these are areas that providers are less knowledgeable in addressing.

To assure the principal investigator remains blind to which participants are in the control vs experimental group several precautions will be taken. The principal investigator will not be involved in the check-in process of the educational program. Additionally, during data collection the tracking information will be routed to the study coordinator. Additionally, any questions initiated through coaching will route to an email that only the study coordinator has access to. The study coordinator will route the email to the PI without any identifying information. The investigator will return the email to the study coordinator with an answer, who will return the answer to the participant. This ensures the investigator will remain blind to which group the participants are in.

Over the course of 6 months the number of contraceptive discussions, number of patients who chose the implant, another reliable method, and no method will be tabulated for the experimental and control groups. Additionally individual providers trends over time for each of these variables will be analyzed for each group.

At the conclusion of the data collection period, five participants from each group will be selected at random to participate in a focus group. This focus group will last 1 hour. It will be audio recorded and analyzed to elicit narrative on barriers to counseling, referring, and managing patients with etonogestrel implant. Focus group participants will be compensated with a \$100 gift card for their time.

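### Material that reveals the arm appears to reach providers before the shared session, so allocation may precede attendance, pre-test and post-test with nothing gained, and the time of randomisation is never stated

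*Protocol*

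**What the plan says.** The Phase 2 Protocol is one continuous text, so places are given by topic.

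- **Design.** "A cohort of 100 providers will be recruited" and "The cohort will be randomized into two groups". No time point or allocation ratio is given. Both groups attend the virtual session together and take the same pre-test at its start and the same post-test at its end. Both also receive "the same written tip sheet at the end of the educational activity". The arms differ only in that the experimental group may use at-will coaching.
- **Recruitment.** Eligibility is confirmed and consent obtained after a provider expresses interest in the event.
- **Educational packet.** Each participant receives "the slides and a troubleshooting tip sheet mailed to them prior to the date of educational event". The text goes on: "Participants who have consented to the study will additionally receive a contraception discussion tracking form", which is colour coded and labelled "to indicate whether the participant has been randomized to the control group or the experimental group". The form has no mailing date of its own. The same paragraph states that the experimental group's tip sheet carries the email address for coaching.
- **Blinding of the principal investigator.** Among the precautions: "The principal investigator will not be involved in the check-in process of the educational program".

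**The concern.** If material that identifies the arm arrives before the event, randomisation has already happened and the provider may know the result. The decision to attend, and the effort put into the session and both tests, can then depend on arm. A provider who consents but misses the session is already in the trial, without the shared education and without the session-based tests.

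The arms are treated identically until the session ends, so no feature of the design needs allocation before that point. The weakness is avoidable.

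**Working it through.** **Step 1: order of events.** The point turns on sequence, so the statements are set side by side.

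| Topic | What it implies about timing |
|---|---|
| Packet: slides and tip sheet | Mailed before the event |
| Packet: experimental tip sheet carries the coaching address | The sheet differs by arm, so if mailed before the event it must follow randomisation |
| Packet: arm-marked form, received additionally | No date of its own; reads as an addition to the packet just described |
| Blinding: investigator kept out of check-in | Makes most sense if allocation could be seen by check-in |
| Design: same tip sheet at the end of the activity | Conflicts with the packet paragraph on timing and on content |

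The first four rows point to allocation before the session. The second does so without relying on when the form is sent. The last row points the other way. Early allocation is therefore the natural reading of the packet paragraph, but the protocol does not state it. What is certain is that the tip-sheet statements contradict each other and that the time of randomisation is not fixed.

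**Step 2: size, for illustration.** The protocol gives 100 providers but no alpha, power, effect size, SD or attendance rate, so there is no planned calculation to reproduce. Assumptions:

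- two-sided alpha 0.05, 80% power, 1:1 allocation, independent providers;
- non-attendance d of 10% to 20%, equal in the two arms;
- non-attenders show no coaching effect but are analysed as randomised.

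*Base, 50 per arm.* The normal approximation gives (1.960 + 0.842) × √(2/50) = 0.560 SD. The t-test value is 0.566 SD and is used below.

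*Randomise before the session and keep everyone.* The average effect shrinks by (1 − d), so the difference that must exist among attenders is 0.566/(1 − d):
- d = 0.10: 0.566/0.90 = 0.629 SD; effective n = 100 × 0.90² = 81
- d = 0.20: 0.566/0.80 = 0.707 SD; effective n = 100 × 0.80² = 64

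*Randomise attenders after the session.* Only 100 × (1 − d) are randomised, so the detectable difference is 0.566/√(1 − d):
- d = 0.10, 90 randomised: 0.566 × √(100/90) = 0.597 SD
- d = 0.20, 80 randomised: 0.566 × √(100/80) = 0.633 SD

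*Avoidable part.* 0.629 − 0.597 = 0.03 SD and 0.707 − 0.633 = 0.07 SD.

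The right comparator is 0.597 to 0.633 SD, not 0.566 SD, because randomising later does not bring absent providers back.

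**The case against.** The strongest reply is that the timing is inferred. The pre-event mailing date is attached only to the slides and tip sheet, the form is undated, and 30 minutes of the session are set aside to explain the study, when forms could be issued. This stands as a limit on the wording. It does not clear the plan, because the experimental tip sheet alone would reveal the arm if mailed as described.

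The second reply is that the harm is small. The outcomes tabulated by group are six months of tracking counts. Neither test is named as an outcome or covariate for the arm comparison. Only the investigator is said to be blinded, and providers must learn their arm eventually in order to use coaching. This largely stands.

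Three stronger readings are tempting, and the document does not support them:

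- **That early allocation spoils both tests as baselines.** The post-test follows the education and was never a baseline. The pre-test has a separate problem in both arms: slides and key take-away points are mailed to everyone beforehand.
- **That non-attenders are automatically lost after randomisation.** Coaching is by email, its address is repeated in the experimental group's reminders, and nothing makes coaching or tracking conditional on attendance. A non-attender can be coached, return forms and be analysed as randomised.
- **That the lack of an analysis rule for non-attenders is itself a fault.** Such rules are commonly left to the statistical analysis plan, which is not shown.

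**Conclusion.** The point holds as a recommended improvement to the design. On the natural reading, arm-revealing material reaches consented providers before the session, so allocation precedes attendance and both tests and may be known to participants. The contradiction over the tip sheet and the missing time of randomisation need correcting on any reading.

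The avoidable loss of precision is about 0.03 to 0.07 SD under the stated assumptions, and smaller if non-attenders use coaching. The more important gain is that attendance and test engagement can no longer depend on arm. The size of any such dependence cannot be computed from the document.

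**What to change.** 1. State when randomisation takes place. Recommended order: consent before the event, pre-test, session, post-test, then randomisation of those who attended.
2. Only after that, send the arm-marked tracking forms and, to the experimental arm, the coaching address.
3. Reconcile the design and packet paragraphs so that one identical tip sheet, without the coaching address, is given at the end of the session.
4. If 100 randomised providers are wanted, allow for absence at consent: 100/0.90 = 111.1, so 112 at 10% non-attendance, or 100/0.80 = 125 at 20%. Both rates are assumptions.

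The cost of the resequencing is a second mailing or an email, and month 1 starts a few days later. It needs no extra visits and leaves the intervention unchanged. Step 4, if adopted, adds recruitment.

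This order does not by itself protect the pre-test from slides mailed in advance. If the pre-test is meant to measure knowledge before education, the slides should be held back as well.

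### The tracking form does not exclude or separate boys, although the study question is about adolescent girls, so three of the four tabulated counts can cover a wider population than the question

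*Protocol*

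**What the plan says.** The protocol has one section, headed Phase 2 Protocol, and four places in it bear on this point.

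- **Study question (opening sentence).** The trial asks how coaching affects "recommendation of the etonogestrel contraceptive implant to adolescent girls considering contraception".
- **Provider eligibility.** The provider "must have a practice that provides care to female patients under the age of 18". The setting may be any of four specialties: "in a pediatrics, family medicine, internal medicine or obstetrics/ gynecology practice that refers patients for or provides contraception in their practice". A practice must include girls but need not be limited to them.
- **Tracking form.** For each day the provider is to "record the number of patients under 18 who they discussed contraception with", followed by "the number who chose the implant, the number who chose another reliable contraceptive method, and number who chose no option".
- **Tabulation (paragraph on the 6-month outcomes).** By group, "the number of contraceptive discussions, number of patients who chose the implant, another reliable method, and no method will be tabulated". Individual providers' trends in the same variables are also to be analyzed.

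The limit to girls appears in the first two places and not in the last two. No instruction to leave boys out appears anywhere.

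**The concern.** The protocol limits its population by sex where it states its question and its entry rule, then drops that limit where it defines what is counted. A provider who follows the form description literally would record a contraception discussion with a boy under 18. He cannot be in the implant cell, so he adds to the discussion total and, depending on how the provider classifies him, to the other-method or no-method cell.

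Three of the four tabulated counts could then move with no change in what happens to girls. Any implant proportion formed with discussions as denominator would be taken over patients who could not receive the implant. Providers may also read the line differently, some counting boys and some not, which adds variation between providers that has nothing to do with coaching.

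This cannot be left to an analysis plan. As described, the form yields daily totals without sex, so boys who have been counted cannot be taken out afterwards.

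**Working it through.** **No figure to reproduce.** The protocol gives a cohort of 100 providers but no rate, effect size, alpha or power. Every number below is an assumption chosen to show scale.

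**Notation.** For one group, G is the number of recorded discussions with girls, B the number with boys, and b = B / (G + B) the boys' fraction. Let p be the implant share among girls.

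**1. Effect on each tabulated count.**

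| Count | Girls only | As the form is worded |
|---|---|---|
| Discussions | G | G + B |
| Chose implant | pG | pG (unchanged) |
| Other reliable method, no method | (1 − p)G in total | (1 − p)G + B in total, if every boy is placed in a cell |

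If coaching leaves B alone, the expected difference between groups in the discussion count is unchanged. Its ratio is pulled toward 1, and the variability of B between providers is added as noise.

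**2. Effect on an implant share per discussion.** The protocol does not name this quantity, but it is a natural summary of these counts.

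Recorded share = pG / (G + B) = p(1 − b).

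With the same b in both groups, the absolute difference is also multiplied by (1 − b), and the ratio of shares does not change. For p = 25%, b of 10%, 20% and 30% gives:

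- 25% × 0.9 = 22.5%
- 25% × 0.8 = 20.0%
- 25% × 0.7 = 17.5%

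**3. Effect on precision.** Assume true shares in girls of 20% and 30%, two-sided 0.05, power 0.8, and independent discussions. Discussions within a provider are in fact clustered, so only the relative change is of interest.

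| b | Recorded shares | Difference | Recorded discussions per group | Of these, girls: n(1 − b) |
|---|---|---|---|---|
| 0 | 20% vs 30% | 10 points | 294 | 294 |
| 10% | 18% vs 27% | 9 points | 337 | 303 |
| 20% | 16% vs 24% | 8 points | 392 | 314 |
| 30% | 14% vs 21% | 7 points | 462 | 323 |

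The ratio stays at 1.5 in every row. The recorded discussions needed rise by 57% at b = 30% (462 / 294 = 1.57), but most of that rise is the boys themselves. If providers see the same girls either way, the number of girls needed rises by about 10% (323 / 294 = 1.10). A constant boys' fraction therefore costs little information, and a fraction that varies between providers costs more.

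**4. When the comparison is biased.** Suppose the true share in girls is 20% in both groups.

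- b = 10% vs 20%: 20% × 0.9 = 18% against 20% × 0.8 = 16%
- b = 10% vs 30%: 20% × 0.9 = 18% against 20% × 0.7 = 14%

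An apparent difference of 2 or 4 points arises with no effect in girls, but only because b differs by group.

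**The case against.** The strongest reply is that nothing says boys will be recorded. The form itself is not shown, and one sentence describes it. The question and the eligibility rule both specify girls, the teaching is about the implant, and 30 minutes of the session are set aside to explain the study. Providers may well read the line as meaning girls. This stands as far as certainty goes: the wording fails to exclude boys, and no more can be said. It does not remove the point, because relying on context lets different providers count differently.

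Second, providers are randomized, so male caseload is balanced in expectation. A reader might infer that differences between pediatric and gynecology practices bias the coaching comparison. The protocol does not support that: such differences are variation between providers. Systematic bias would need coaching to change how often boys are counseled or recorded. Nothing suggests it does, since the coaching question categories concern implant indication, procedure and post-placement effects. For individual providers' trends over time, a stable male caseload largely cancels.

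Third, the count closest to the question, the number choosing the implant, is untouched, and the protocol names no implant share. Both statements are correct. A reader might infer that the trial's main outcome is corrupted. It is not; three of the four tabulated counts are open to contamination.

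Fourth, the protocol does not say which methods count as reliable, so the cell in which a boy would be placed is unknown. That also stands.

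**Conclusion.** The mismatch is real on the text. The form counts patients under 18 with whom contraception was discussed, not all minors seen, and does so without regard to sex, while the stated question is about girls. Followed literally, this measures the discussion, other-method and no-method counts in a population wider than the question.

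The size is unknown, because the protocol gives no rates and no male caseload. On assumed boys' fractions of 10% to 30%, equal in both groups, an absolute difference in implant share per discussion shrinks to 0.9 to 0.7 of its value, with the ratio of shares and the implant count unchanged. The expected result is dilution and noise, and bias only if the boys' fraction differs by group.

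The protocol does not support stronger statements that boys will be counted or that the comparison is biased. Severity is minor and confidence moderate. The reason to act is that the fix is nearly free now and impossible once the totals are collected.

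**What to change.** Before the packets are mailed, change the form line to 'number of female patients under 18 with whom you discussed contraception'. Restrict the three choice counts to those patients, and make the same restriction in the paragraph that describes the 6-month tabulation and provider trends. If the sponsor wants to keep information on boys, record each count separately by sex and tabulate the girls' counts for the study question.

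With the first option, the only cost beyond a changed line is that discussions with boys, which lie outside the stated question, are no longer counted. The second option costs extra columns for the provider to fill in each day.

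### Does pointing the weekly reminder at the MOC portal lose counts from providers who cannot earn MOC credit?

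*Protocol*

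**What the plan says.** All of this stands under the single heading Phase 2 Protocol.

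- **Recruitment.** The cohort is 100 providers, with a floor on non-physicians: "A minimum of 30% APRN or PA providers will be recruited".
- **Credit.** Under the CME arrangements, "study participants who are physicians and hold board certification can elect to receive Part 4 Maintenance of Certification credit".
- **Materials.** Consented participants receive a tracking form for each study month, coloured by group. The list of what they receive continues: "As well as instructions on how to enroll in the MOC program". No profession is excluded.
- **Return by email.** The form carries an "email address at the bottom that the participant should use to return in their contraception discussion tracking forms". That sentence calls the sheet a referral form, but what is returned is plainly the tracking form.
- **Portal entry.** "Each week participants will receive an email reminding them to enter the information from the tracking form into the MOC portal". The experimental group's coaching address travels with the same prompt: "this email will be included in all communication reminding them to enter their tracking form information into the MOC portal".
- **Routing and use.** The blinding paragraph says that "during data collection the tracking information will be routed to the study coordinator". The next paragraph says that over six months the "number of contraceptive discussions, number of patients who chose the implant, another reliable method, and no method will be tabulated" by group, and that individual providers' trends will be analysed. Neither paragraph names the form or the portal as the source.

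**The concern.** The same daily counts have two routes to the study team, and the only one with a stated reminder is a portal named after a credit that many participants cannot earn. APRNs and PAs are outside the credit offer, as are physicians who lack board certification or choose not to claim it. If the portal fed the analysis and these providers responded less to its reminder, their counts would be less complete, and the results would represent the intended mix of professions less well. These self-reported counts are what the protocol tabulates, so their completeness matters. It is also fair to ask which record prevails if a provider's form and portal entry disagree. A statistical analysis plan could answer that, but it could not recover counts that nobody was prompted to send.

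**Working it through.** The protocol gives no power, effect-size or completeness figure on this point, so there is nothing of its own to reproduce. The check is mainly a reading of the text, with simple arithmetic to bound the size.

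**Step 1: who is outside the credit offer.** Inputs: cohort 100 and APRN/PA minimum 30%, both from the recruitment paragraph. 0.30 × 100 = 30 providers at least. Physicians without board certification, or who do not elect the credit, add to this in a number the protocol does not give.

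**Step 2: is anyone kept off the portal?** Set the credit sentence beside the materials and reminder sentences. The first limits who may receive credit. The other two give enrolment instructions and reminders to participants without a limit by profession. Together they say that all are told how to enrol, all are reminded to enter data, and some earn credit. These statements do not contradict one another.

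**Step 3: is there a route that does not depend on MOC?** Yes, the emailed form. It identifies the group by colour and the month by label, which are the two keys needed to tabulate by group and follow trends over time. The blinding paragraph sends the tracking information to the study coordinator, which fits an emailed form. This is the most natural reading, although the protocol does not say so outright.

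**Step 4: size under the least favourable assumption.** Suppose the portal were the only source, exactly 30 APRN/PAs were recruited, a fraction f of them entered nothing, and a fraction g of the 70 physicians entered nothing. Both f and g are assumptions.

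- Contributors = 100 − 30f − 70g
- APRN/PA share = (30 − 30f) / (100 − 30f − 70g)

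| f | g | Contributors (expected) | APRN/PA share |
|---|---|---|---|
| 0 | 0 | 100 | 30.0% |
| 0.25 | 0 | 92.5 | 22.5/92.5 = 24.3% |
| 0.50 | 0 | 85 | 15/85 = 17.6% |
| 1 | 0 | 70 | 0% |
| 0.50 | 0.25 | 67.5 | 15/67.5 = 22.2% |
| 0.50 | 0.50 | 50 | 15/50 = 30.0% |

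The rows with g = 0 are the worst case for professional mix, because they let no physician lapse. Yet physicians who do not elect MOC have the same lack of incentive. Once they lapse too, the share moves back toward 30%, although the total falls further.

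**Step 5: is the 30% minimum breached?** No. It governs recruitment. One silent APRN/PA would give 29/99 = 29.3% among contributors, but the protocol sets no floor for contributors.

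**Step 6: the other reading.** If the emailed forms are the source, failure to use the portal removes nothing, and the loss by this mechanism is zero for every f and g.

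**The case for a change.** The strongest case for a change is that this is trial conduct, not analysis. The protocol itself fixes the reminder's content, and fixes it on a system tied to a credit that at least 30 of 100 providers are not offered. The email route has no stated reminder or return interval, and the routing sentence is compatible with emailed forms without naming them. A one-sentence clarification would be cheap.

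Part of this stands. The reminder does name only the portal, the source of record is not named, and no rule ranks the two records if they differ. The rest does not carry. Nothing in the protocol suggests that providers without a credit to earn ignore a weekly email; that is a conjecture about behaviour. The reminder also refers to the tracking form itself, so it prompts every participant about the counts each week whichever route is used.

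Redirecting the reminder has costs of its own. It would remove the only stated portal prompt for physicians who do want the credit. It would tie a weekly message to a month-labelled form whose return interval is not stated. If emailed forms were declared the record, the coordinator would transcribe up to 100 × 6 = 600 of them.

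**Conclusion.** No change to the plan is needed. Followed as written, it gives every participant two ways to submit the same counts, at least one of which has no connection to MOC credit, and it excludes no one from the other. Loss of data is possible in any self-reported study, but the text does not show it here. The losses worked out above apply only if the portal is the sole source, which runs against the stated email return, and the largest shifts in professional mix also assume that no physician lapses. Otherwise the effect is zero. Both arms share the same routes and reminders, so the comparison of coaching with standard education is not biased by this feature, and no power figure depends on it.

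The silence on which record is tabulated is a gap in detail. It is commonly settled in data-handling documents or the analysis plan, which is not shown here, and a coordinator holding group-coded, month-labelled forms can fill it sensibly. This conclusion rests on reading the credit restriction as a limit on credit alone. If the portal in fact refused non-physicians, the emailed form would still collect their counts.
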